#### **4.2 Per-protocol (PP) Cohort**

The per-protocol (PP) population is all mITT subjects who:

1. meet critical study eligibility criteria;
2. have no significant protocol deviations that could affect the validity of data; and
3. have evaluable assessment for the endpoint of interest.

A significant protocol deviation means non-adherence on the part of the subject or investigator to clinically significant protocol-specific inclusion/exclusion criteria, primary objective variable criteria or critical study requirements that could affect the scientific validity of the observed data point or lead to bias. Missing data are not imputed for analyses with the PP cohort.

#### **4.3 Safety Cohort**

The safety analysis population includes all subjects in whom Aquablation is initiated. This cohort is used for most safety analyses.

---

\* See <https://cran.r-project.org/>

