### ***2.24 Case Report Forms (CRF)***

Data will be entered into an EDC system. If a consented subject is not treated, a study exit form will be completed to record the reason for screen fail or withdrawal.

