### ***5.2 Potential Risks***

The AQUABEAM System is used during a surgical procedure on the lower urinary tract. Risks associated with surgical procedures, some of which could be fatal, include:

- Irritative symptoms of urgency, hesitancy, dysuria, and nocturia
- Bleeding
- Lower urinary tract infection
- Bladder, rectum, or prostate injury
- Reaction to anesthesia
- Sphincter damage
- Urinary extravasation
- Swelling or irritation of the prostate, bladder, perineum, or urethra
- Pain
- Changes in ejaculatory function
- Reproductive system disturbances
- Blood Transfusion
- Perforation

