#### **4.1 Modified Intent-to-Treat (mITT) Cohort**

The mITT population includes all enrolled subjects in whom the Aquablation handpiece is inserted into the penile urethra. A patient found at the time of the procedure to have a condition that results in study exclusion does not contribute to the mITT cohort. The mITT population is the primary analysis population for both the primary safety and effectiveness endpoints.

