## 5.2 Primary Safety Endpoint

The study's primary safety endpoint is the proportion of subjects with adverse events rated as probably or definitely related to the study procedure classified as Clavien-Dindo Grade 2 or higher or any Grade 1 event resulting in persistent disability (e.g. incontinence, ejaculatory disorder, or erectile dysfunction) evidenced through 3 months post treatment. Note that the Clavien-Dindo classification scheme is for grading postoperative complications, not events that reflect lack of treatment efficacy. The endpoint is adjudicated by the study's clinical events committee (CEC).

The study's primary endpoint hypothesis is a one-way statistical test (alpha=.025 for interpretation):

$$\begin{aligned}
 H_0: \text{Mean (safety rate at 3 months)} &\geq 65\% \\
 H_a: \text{Mean (safety rate at 3 months)} &< 65\%
 \end{aligned}$$

An exact binomial test (binom.test in R) will be used to determine the P-value for the above comparison. Power calculations showed that the primary safety endpoint with 90 evaluable subjects has an 80% power to detect a safety rate of less than 65%.

The primary safety endpoint is calculated using the mITT population.

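### The SAP's Safety cohort starts later than its mITT cohort, so men harmed before the waterjet starts drop out of the analyses run on it, although harm from handpiece insertion onward still counts in the primary safety endpoint

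*SAP*

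**What the plan says.** The SAP defines two cohorts with different entry points.

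- **mITT (SAP 4.1):** "The mITT population includes all enrolled subjects in whom the Aquablation handpiece is inserted into the penile urethra". One sentence removes men from it: "A patient found at the time of the procedure to have a condition that results in study exclusion does not contribute to the mITT cohort".
- **Safety (SAP 4.3):** "The safety analysis population includes all subjects in whom Aquablation is initiated". On its use the SAP adds: "This cohort is used for most safety analyses".

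The primary safety endpoint is not run on the Safety cohort. SAP 5.2 says "The primary safety endpoint is calculated using the mITT population", and SAP 4.1 agrees. The SAP does not list which analyses make up the rest. SAP 7 plans summaries of Clavien-Dindo grades at month 3 (item 1) and of device- or procedure-related events (item 11) without naming a cohort.

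Four parts of the protocol bear on this:

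- Section 2.4 (Handpiece) describes the tip being passed through the prostatic urethra into the bladder and positioned, and only then the start of Aquablation.
- Section 5.2 lists reaction to anesthesia, perforation and "Bladder, rectum, or prostate injury" among the risks.
- Section 2.24 says: "If a consented subject is not treated, a study exit form will be completed to record the reason for screen fail or withdrawal". It does not define *treated*.
- Section 2.20 has all adverse events documented in all study subjects during treatment and through 12 months.

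**The concern.** A safety population is normally at least as wide as the efficacy population, because its purpose is to capture everyone exposed. Here it is narrower at the point of entry. The gap is a real period of exposure: by the time the jet starts, the man is under anesthesia (Protocol 2.16) and the handpiece has been advanced into the bladder under ultrasound and cystoscopic guidance.

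A case abandoned in that gap may have been abandoned because access went wrong. Leaving such men out can only remove access-related harms from the tables, so for those harms the bias runs toward fewer reported events. The protocol's own definitions treat these harms as relevant. Table 3 counts events arising from deployment of the device or from user error as adverse device effects, and Table 4 grades relatedness to the procedure as well as to the system.

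**Working it through.** **1. The plan's own safety figure.** Inputs from Protocol 4.2 and SAP 5.2: null rate 65%, assumed true rate 50%, 90 evaluable men, one-sided alpha 0.025, exact binomial test, stated power 80%.

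- Largest passing count: P(X ≤ 49 | n = 90, p = 0.65) = 0.0248, while 50 events gives 0.0401. The test passes at 49 or fewer.
- Power: P(X ≤ 49 | n = 90, p = 0.50) = 82.9%.
- A normal approximation using the variance at 50% gives 81.2%. With null and alternative variances and a continuity correction it gives 80.8%.

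The stated 80% is reproduced, slightly on the cautious side. The cohort definition does not affect it.

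**2. Cohort membership by the time of harm.**

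| Time of harm | mITT (primary safety endpoint) | Safety cohort |
|---|---|---|
| Before handpiece insertion (anesthesia, intraoperative ultrasound), ablation never started | Out, if the handpiece is never inserted | Out |
| At or after insertion, ablation never started | In, unless removed by the SAP 4.1 exclusion sentence | Out |
| Any time, ablation started | In, unless removed by the same sentence | In |

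The order of insertion and initiation comes from Protocol 2.4. That anesthesia and intraoperative ultrasound precede insertion is an assumption; the documents do not set out that order.

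**3. Size of the effect on a Safety-cohort rate.** Suppose x of N men have an event. Dropping one man who had an event lowers the rate by

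x/N − (x − 1)/(N − 1) = (N − x) / [N(N − 1)].

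With N = 101:

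- x = 50: 51 / (101 × 100) = 0.50 percentage point.
- x = 55: 46 / (101 × 100) = 0.46 percentage point.
- x = 1 (a rare event): 100 / (101 × 100) = 0.99 percentage point, that is 1/101 against 0/100.

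The documents do not say how many men had insertion without ablation, so the number k is varied. Take 101 mITT men with 55 events, the largest passing count (54.5%, exact p = 0.0184), and let all k men have an event:

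| k | mITT | Safety cohort | Difference (points) |
|---|---|---|---|
| 0 | 55/101 = 54.5% | 55/101 = 54.5% | 0 |
| 1 | 55/101 = 54.5% | 54/100 = 54.0% | 0.5 |
| 2 | 55/101 = 54.5% | 53/99 = 53.5% | 0.9 |
| 3 | 55/101 = 54.5% | 52/98 = 53.1% | 1.4 |
| 5 | 55/101 = 54.5% | 50/96 = 52.1% | 2.4 |

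The mITT column does not move, so the narrower Safety cohort leaves the primary test as it is.

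**4. The follow-up question.** Suppose, as an assumption, that 3 men with insertion but no ablation are added to 101 treated men of whom 52 have events. Exact one-sided p-values against 65%:

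- All 3 have events and these are found: 55/104 = 52.9%, p = 0.0072.
- None of their events is found and they count as event-free: 52/104 = 50.0%, p = 0.0012.

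Both pass; the limit at n = 104 is 57 events (p = 0.0202). With 3 men, missed events could change the result only if the true count were 58 to 60.

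**The case against.** A reader might infer that men harmed at handpiece insertion vanish from safety analysis altogether. The documents do not support that. Insertion is what admits a man to mITT, and mITT is the population for the only safety analysis with a hypothesis and a pass mark. What he drops out of is the group of analyses run on the Safety cohort. Even that, for the SAP 7 tables, is an inference from SAP 4.3, because those items name no cohort.

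A reader might also infer that Protocol 2.24 ends follow-up for a man whose procedure is aborted after insertion. It does not say so. The sentence sits under case report forms, speaks of recording a reason for screen failure or withdrawal, leaves *treated* undefined, and does not say that adverse-event follow-up stops. Protocol 2.20 points the other way. Most of the harms in question would also arise around the procedure, and Table 2 collects adverse events at treatment and at discharge. What stands is an ambiguity: Protocol 2.25 treats withdrawal as the end of participation, so a man labelled in that way could be exited while still in mITT for a 3-month endpoint.

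The number of such men may well be zero. Protocol 2.2 reports that all 84 earlier procedures were technically successful. With 0 of 84 the one-sided 95% upper bound is 1 − 0.05^(1/84) = 3.5%, although those prostates averaged 49.8 mL against the 80–150 mL treated here. This objection bears on size. It does not remove the mismatch between the two definitions.

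**Conclusion.** The concern holds in a limited form. The Safety cohort starts later than mITT and omits men already exposed to the procedure. Men harmed between insertion and initiation stay in the primary safety endpoint, subject to the SAP 4.1 exclusion sentence, but leave analyses run on the Safety cohort. Men harmed earlier, whose procedure stops before insertion, are in neither cohort.

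Each omitted man with an event costs about 0.5 percentage point on a rate near 50%, and about 1 point on a rare event. No change to the primary test is expected. The sizes rest on N of about 101 and on assumed counts of aborted cases, which the documents do not give. The case for amending rests on the direction of the bias, on rare serious harms such as perforation or rectal injury, and on how little the change costs. Loss of follow-up under Protocol 2.24 is a possible reading, not a stated rule.

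**What to change.** 1. **SAP 4.3.** Define the Safety cohort as all men in whom anesthesia for the study procedure is begun, or in whom the handpiece or the intraoperative ultrasound probe is inserted. Exclude the baseline screening ultrasound explicitly; otherwise men who were never operated on would enter. The cohort then contains mITT, and it keeps for safety reporting any man removed from mITT by the SAP 4.1 exclusion sentence. Starting at handpiece insertion would be the minimum needed to match the mITT entry point, but would leave out harm before insertion.
2. **SAP 7.** Name the cohort for items 1 and 11. Add a listing of aborted procedures with the reason and any adverse events, and report the number even if it is zero. Protocol 2.11 gives the sample as men who have already received treatment, so this can be done from existing records.
3. **Protocol 2.24.** Define *treated*, and reconcile the sentence with Protocol 2.20 and SAP 4.1 so that a man in mITT with an aborted procedure is not exited before the 3-month safety assessment.

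The cost is a few sentences in the two documents and, possibly, adverse-event follow-up of a few men. Reported event rates may rise slightly.

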## **5 STUDY ENDPOINTS**

### **5.1 Primary Effectiveness Endpoint**

The primary effectiveness endpoint is the IPSS change score from baseline to 3 months. IPSS is an accepted and commonly used measure for symptom severity in BPH. IPSS varies from 0 (no symptoms) to 35 (maximal symptoms). The mean 3-month IPSS change score (abbreviated dIPSS3) in WATER was 16 points (SD=7 points). WATER used a non-inferiority margin of 5 points; 5 points represents the minimum change for men with moderate-to-severe BPH that is detectable. The current study's goal is therefore to show that the IPSS change score statistically exceeds 16-5 = 11 points. The study's hypotheses are therefore:

$$\begin{aligned} H_0: \text{dIPSS}_3 &\leq 11 \\ H_a: \text{dIPSS}_3 &> 11 \end{aligned}$$

A one-way t test with the mITT cohort will be used for the calculation. With 100 patients and assuming 10% subjects lost to follow, 90 evaluable subjects with an underlying change of 16 points and a change score SD of 7.5 points yields a 99% power to detect an improvement of more than 11 points.

A secondary goal is to show similarity of change scores between WATER II and WATER. Data from WATER and WATER II will be combined. Regression analyses controlling for baseline IPSS score (a strong predictor of change scores) will calculate differences in change scores between WATER and WATER II subjects. WATER II will be determined to have similar dIPSS3 scores if the 95% confidence limits for the difference between WATER and WATER II Aquablation subjects exceeds -5 points. The study is not necessarily powered for this comparison.

Missing data for dIPSS3 will be imputed using the following rules:

- Predicted value from baseline IPSS: In WATER, dIPSS3 was strongly and statistically significantly related to baseline IPSS (Figure 1). This finding is not surprising for maximally effective procedures that reduce scores to close to maximal (i.e., a ceiling effect). A linear regression model using WATER II available data will be used to predict missing change scores.
- Low value: A change score of 0 points
- High value: a change of 5 less than the maximal possible improvement, which represents change scores from WATER (see also Figure 1)

[figure not shown]

Figure 1. Relationship between baseline IPSS and 3-month change score in WATER. Blue = Aquablation, red = TURP.

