### ***4.2 Primary Endpoint Calculation and Sample Size Determination***

Prior studies have shown that IPSS scores are reduced by approximately 16 points after Aquablation, values similar to those observed after TURP. In patients with moderate-to-severe BPH, the mean change in IPSS score representing slight improvement is approximately 5 points. Therefore, showing a mean reduction in IPSS scores that statistically exceeds  $16-5 = 11$  points will be interpreted as study success. The study's primary endpoint hypothesis is a one-way statistical test (alpha=.025 for interpretation):

$$\begin{aligned} H_0: \text{Mean(IPSS change score at 3 months)} &\leq 11 \\ H_a: \text{Mean(IPSS change score at 3 months)} &> 11 \end{aligned}$$

With 100 patients and assuming 10% subjects lost to follow, 90 evaluable subjects with an underlying change of 16 points and a change score SD of 7.5 points yields a 99% power to detect an improvement of more than 11 points.

The WATER study (IDE#G150089) used an assumption that a TURP rate for the same safety definition provided in this protocol would be 65% for a range of prostate sizes 30-80mL. The same safety target will be used for this protocol treating large prostates of 80-150mL. The assumed true rate for the Aquablation patients will be 50% (10% greater than WATER in order to account for treating larger prostates). The study's primary endpoint hypothesis is a one-way statistical test (alpha=.025 for interpretation):

$$\begin{aligned} H_0: \text{Mean (safety rate at 3 months)} &\geq 65\% \\ H_a: \text{Mean (safety rate at 3 months)} &< 65\% \end{aligned}$$

The primary safety endpoint with 90 evaluable subjects has an 80% power to detect a safety rate of less than 65%.

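### Missing 3-month IPSS changes are filled with a single regression prediction and tested with an ordinary t test, which understates the standard error; the SAP also does not say which of its three fill-in rules decides success

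*SAP*

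**What the plan says.** SAP 4.1 fixes the population: "The mITT population is the primary analysis population for both the primary safety and effectiveness endpoints". SAP 5.1 fixes the test of mean improvement against 11 points: "A one-way t test with the mITT cohort will be used for the calculation". SAP 5.1 gives no alpha for this endpoint; Protocol 4.2 does: "one-way statistical test (alpha=.025 for interpretation", that is, one-sided 0.025.

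SAP 5.1 then lists three rules for missing change scores:

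- The first is a prediction from baseline IPSS: "A linear regression model using WATER II available data will be used to predict missing change scores".
- The second is a pessimistic constant, worded as "Low value: A change score of 0 points".
- The third is an optimistic fill that depends on each man's baseline, worded as "High value: a change of 5 less than the maximal possible improvement".

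Neither document mentions a residual draw, multiple imputation or a variance correction. Neither says which rule feeds the deciding test, or that the second and third are sensitivity analyses. The protocol has no missing-data rule for this endpoint. The only other imputation statement is in SAP 4.2: "Missing data are not imputed for analyses with the PP cohort". That analysis is not primary, and it also drops men with significant protocol deviations.

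**The concern.** There are two separate problems.

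**Standard error.** On the plain reading, each missing score is replaced by its fitted value and the completed data go into a t test as if all 101 values had been observed. Fitted values lie on the regression line, so they reduce the sample SD while raising n. The standard error comes out too small, and the true one-sided error exceeds 0.025 by an amount that grows with the missing fraction. This applies to the regression rule only.

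**Choice of rule.** Three fills give three tests. If the result falls short of plan, the same data can pass under one rule and fail under another. For a single-arm pivotal study meant to support marketing claims, that choice should not be open when the data are seen.

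**Working it through.** **Inputs.** Null value 11, planned mean 16, SD 7.5 and 10% loss giving 90 evaluable (SAP 5.1); one-sided alpha 0.025 (Protocol 4.2); 101 treated men (Protocol 2.11). Assumptions: all 101 are in the mITT cohort, 11 are missing (close to the planned 10%), and data are missing at random. SAP 5.1 calls the relation to baseline IPSS strong but gives no R-squared, so 0.3, 0.5 and 0.7 are assumed.

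**The plan's own figure.** With 90 evaluable, the noncentrality is (5/7.5) × √90 = 6.32, and power at one-sided 0.025 is above 99.9%. The stated 99% is met.

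**Standard error after regression fill.** Let n = 101, with n_obs observed and n_mis filled.

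- Reported by the t test: SE² = σ²(n_obs + n_mis·R²)/n²
- True: SE² = σ²[R²/n + (1 − R²)/n_obs]

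At R² = 0.5 with 11 missing:

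- reported SE² = 56.25 × 95.5/10,201 = 0.527, so SE = 0.726;
- true SE² = 56.25 × (0.5/101 + 0.5/90) = 0.591, so SE = 0.769;
- ratio 0.944; one-sided error = 1 − Φ(1.96 × 0.944) = 3.2%.

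Across the range:

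| Missing of 101 | Error, R² = 0.3 | R² = 0.5 | R² = 0.7 |
|---|---|---|---|
| 5 | 2.9% | 2.8% | 2.7% |
| 11 | 3.5% | 3.2% | 2.9% |
| 20 (twice plan) | 4.7% | 4.0% | 3.3% |

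With 11 missing, the SE ratios by formula are 0.922, 0.944 and 0.966. Simulation at a true mean of 11 gives 0.917, 0.942 and 0.962, so the SE is about 8%, 6% and 3–4% too small. In a parallel simulation (100 men, 10 missing), a t test on the observed men alone stayed at about 2.5%, so the excess comes from the fill-in step. Multiple imputation from the same regression with 11 missing (50 imputations, Rubin's rules) gave 2.5% at all three R-squared values.

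**Dependence on the rule.** Let m be the mean of the 90 observed men (SD 7.5) and v the average fill for the 11 missing.

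- Completed mean: M = (90m + 11v)/101
- Sum of squares: SS = 89 × 7.5² + 90(m − M)² + 11(v − M)², plus 11·R²·7.5² under regression
- t = (M − 11)/√(SS/100/101)

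Regression takes v = m (missing men with the same mean baseline). Low takes v = 0. High needs a mean baseline IPSS, which is assumed: 21, 23 or 25, less 5, gives fills of 16, 18 or 20.

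| Rule | Observed mean needed for p ≤ 0.025 |
|---|---|
| High (fill 16 / 18 / 20) | 11.98 / 11.77 / 11.57 |
| Regression (R² 0.3 to 0.7) | 12.42 to 12.46 |
| Low | 14.20 |

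Example at m = 13.5:

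- Regression (R² = 0.5): M = 13.5, SE = 0.725, t = 3.45, p = 0.0004.
- Low: M = 90 × 13.5/101 = 12.03, SE = 0.820, t = 1.26, p = 0.106.

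At m = 16 all three rules succeed. Low first fails there with 21 of 101 missing (p = 0.037; with 20 missing, p = 0.02498).

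**The case against.** The strongest reply is that neither problem is likely to change the result. With 11 missing, regression fill needs an observed mean of about 12.42 to 12.46. The multiple-imputation half-widths of 1.55, 1.53 and 1.51 put that threshold at about 12.55, 12.53 and 12.51. The SE error therefore decides the outcome only in a window about 0.05 to 0.13 points wide. If the true mean is 16 (SE 7.5/√90 = 0.79), the chance of landing there is below 1 in 100,000. That stands as a statement about practical weight. It does not answer the error-rate point, which concerns a true mean at 11; high power at 16 gives no protection there.

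A second reply is that the low and high fills are plainly bounds. The regression rule comes first, carries its own rationale, and cannot be applied to the same score together with the other two. That is the natural reading. But the SAP introduces all three as imputation rules and never ranks them. If regression is the base case, the SE problem falls directly on the primary test.

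Third, a strong relation to baseline points to the smaller errors in the table, and multiple imputation does not deal with informative dropout. Both are fair. The low fill already stress-tests informative dropout and should stay, labelled as such.

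**Conclusion.** The concern holds on both counts. As written, the regression rule gives a standard error that is modestly too small: about 3% to 8% with 11 of 101 missing, for a one-sided error of about 2.9% to 3.5% against 2.5%. These figures assume data missing at random and an R-squared between 0.3 and 0.7.

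The unnamed deciding rule has the larger potential effect. With 90 observed and 11 missing, the three rules disagree for observed means of about 11.8 to 14.2 (1.8 to 4.2 points below plan, high fill taken as 18), and regression and low disagree from about 12.4 to 14.2. Below that range all rules fail; above it all succeed. At the planned mean of 16 with about 10% missing, the conclusion is the same under every rule. This should be corrected, but it does not undermine the planned case.

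**What to change.** In SAP 5.1, name one mITT analysis as the primary success test and state that success is judged on it at one-sided 0.025. It should carry the imputation uncertainty. One option is multiple imputation from the SAP's own baseline-IPSS regression, with residual and parameter draws (for example 50 imputations combined by Rubin's rules). Another is an equivalent baseline-adjusted model on the observed data with valid standard errors. Label the low and high fills as sensitivity analyses.

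The cost is a few sentences and standard R code. With 11 missing, the 95% confidence interval half-width grows from 1.42, 1.44 and 1.45 points to 1.55, 1.53 and 1.51 (R-squared 0.3, 0.5 and 0.7), an increase of 0.06 to 0.13 points.
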